8.0 Diversity, Equity, and Inclusion

- **8.1 Explain how the research plan (recruitment, study population, data collection, etc.) is equitable and represents the demographic makeup for the location in which the research will be conducted.**

This study recruits from the general population seeking treatment for chronic pain in Tucson. There are no exclusionary criteria based on any demographic makeup. All demographics in the population being recruited have an equal opportunity to participate in this study.

- **8.2 Describe whether non-English speaking subjects will be included in the study. If yes, please explain how your research team is prepared to meet the needs of the population. If not, please explain why non-English speakers will be excluded from the study population.**

An inclusion criteria is to be able to read and speak English, as parts of the study material require one to understand English.

9.0 Consenting Process:

- **Indicate the informed consent process(es) and/or document(s) for the study. Check all that apply.**

Written Consent
 Informed Consent (ICF) – written or electronically signed form
 Parental Permission – written or electronically signed form
 Assent (participants under 18) – written or electronically signed form
 Combined ICF/PHI Authorization – written or electronically signed form
 Protected Health Information [2] Authorization – written or electronically signed

IRB Protocol for Human Subjects Research

 Translated Consent/Assent – written or electronically signed form(s)
 Short Consent Form – written or electronically signed form (see guidance on Short Form process)
 Debriefing Script or Form – document used to properly inform subjects of the study’s purpose when intentionally deceived

Oral/Online/Unsigned Consent
 Informed Consent – oral script/online/unsigned
 Parental Permission – oral script/online/unsigned
 Assent – oral script/online/unsigned
 Translated Consent/Assent – oral script/online/unsigned

Waivers of Informed Consent and/or PHI Authorization
 Waiver of Consent
 Full Waiver of PHI Authorization
 Partial Waiver of PHI for Screening Purposes

- **Describe in detail the consent processes checked above, including any waiting period for subjects to sign the consent, steps to minimize the possibility of coercion or undue influence, and the language used by those obtaining consent.**

The subjects will be asked to sign an electronic informed consent form during their first study visit. Prior to coming in for the first visit, they will be provided an electronic copy of the informed consent and will have the opportunity for any questions regarding the consent prior to the initial visit where they will sign. Upon signing they will receive a paper copy of their signed consent. The electronic consenting will be done in Qualtrics.

- **Where will the original signed consent and PHI authorization documents be stored?**

The electronic informed consent will be stored in a protected UA Box Health.

- **Acknowledgement of consent form storage.**

 I will store original signed consent and/or PHI authorization documents for at least 6 years past the time the study is concluded.
 For studies involving minors, I will store original signed consent and/or PHI authorization documents for at least 6 years after the youngest participant turns 18.
 Not applicable – I am not collecting signed documents.

10.0 Research and Data Collection Procedures:

- **Select the methods of data collection that will be used in this study (select all that apply):**

IRB Protocol for Human Subjects Research

 Anthropometric measures (e.g., height, weight, waist circumference, etc.)	 Participant observation
 Audio/video recording	✓ Screening data
 Benign interventions	 Self-health monitoring (e.g., pedometers, food diaries, etc.)
 Biological specimens – blood draws	 Surveys – paper
 Biological specimens – clinically discarded blood or specimens	X Surveys – internet (including online and email-based data collection)
 Biological specimens (urine/feces, tissue, saliva, skin, hair, nails, nasal swab)	 Surveys – telephone
 Clinical Data Warehouse (CDW)	X Randomization with control and experimental groups
 Cognitive or behavioral measures, including daily diaries	 Records – billing
 Data collected using other communication/electronic devices (e.g., cell phones, pagers, and texting devices)	 Records – educational
 Data previously collected for research purposes	 Records – employee
 Deception	 Records – lab, pathology and/or radiology results
X Instrumentation, equipment, or software not approved by the FDA	 Records – mental health
 Interviews – focus groups	 Records – substance abuse
 Interviews – in person	 Research imaging protocols
 Interviews – virtual/online	 Recombinant DNA
 Medical records review	 Social networking sites
 MRI/ultrasound with contrast	 Stem cells
 MRI/ultrasound without contrast	 Radiation Scans (X-Ray, CT Scans, etc.)
✓ Non-invasive instruments (e.g., external sensors applied to the body)	X Other activities or interventions – describe: We will collect EEG data, Vitals (heart rate, blood pressure, Pulse O2, respiratory rate, and temperature), responses to pain surveys (VAS and FACES) as well as responses to a cognitive evaluation (MMSE). Click or tap here to enter text.

- **Description of research procedures.**

The proposed study employs a randomized, double-blind, sham-controlled design to evaluate the effects of the tDCS using the tKIWI device on chronic pain. We will be randomly assigned to treatment (tx) or sham/placebo group.

IRB Protocol for Human Subjects Research

Up to 40 participants will be recruited and randomly placed in either the treatment or the sham group. The randomization ratio is 1:1. Each participant has an equal chance of being assigned to each condition and each participant will be assigned to a condition independently of the other participants. The sample is small (20 each group), so in order to ensure random assignment, we will assign a unique number to every participant of the study's sample. Then, we will use a lottery method to randomly assign each number to the control or experimental group.

The screening will be in redcap where the potential participant will respond to inclusion and exclusion criteria. If the participant is eligible, they will be emailed or provided the consent and enrolled in the study. They will sign the consent during their first visit where demographic data will also be collected and entered into Qualtrics.

Demographics Collected will include:

- Age
- Sex
- Race/Ethnicity
- City, State, Zip
- Phone
- Email
- First Drug Use
- Most Recent Drug Use
- Preferred/Most commonly used drug
- Mental Health diagnoses (including SUD)

The study will occur in 7 visits over an 11 day-period. (see table 2). At the beginning of each visit, the participants will answer a very brief “Pre-Study Session Update” survey to ensure no changes to eligibility have occurred between visits.

Visit 0 will consist of informed consent review and signature, collection of demographic data, baseline self-report pain using the pain surveys (FACES and VAS), brief cognitive survey (MMSE), and baseline EEG recording.

Visits 1-5 will consist of initial EEG recording, three sessions of ramped up tDCS followed by EEG recording and self report pain surveys. Session 1 will be 5 minutes, session 2 will be 5 minutes, and session 3 will be 10 minutes. Details on mAs are listed under tDCS application. The final post visit (V7), on day 11 will consist of no treatment, but a repeat of the data collected on Visit 0.

The visits will take place in [name] lab, room 645 in the UArizona Life Sciences Building. This laboratory is approximately 600sq/ft in size. All [name]’s labs are located next to each other in the Life Sciences North building (Rms 632, 621, 619, 614, 615, 601). All biohazards are disposed according to institutional guidelines. Through [name], we will also have access to shared laboratories that include a molecular biology laboratory of 1,000 sq. ft, an analytical laboratory of 1500 sq. ft. and a radioligand binding laboratory of 1,000 sq. ft. The laboratories include seating space for students and research personnel.

Clinical Trial Protocol: Baseline V0, Tx V0-5, Post V7 (11 days)	
⇒	Pre-Questionnaire (15 min) 
 ○ Cognitive Eval (MMSE) ○ Rate Pain (VAS & FACES) ○ Record medication, activity, symptomology past 24 hours
⇒	Monitor vitals (5 min) 
 ○ HR, BP, PulseO², respiratory, temp, etc (set up continuous measure) ○ Put on device and log into patient portal
⇒	EEG Recording (5 minutes)
⇒	Treatment/Sham (20 min max)
⇒	EEG Recording (5 min) 
 ○ Rate pain using VAS & Faces) ○ Record symptoms, side effects, complaints
⇒	Visit 11, 5-day lapse return for EEG and VAS and FACES

IRB Protocol for Human Subjects Research

Table 2. Study Visit Schedule T-Arm and P-Arm	
V0 Baseline Week 1	
 • Consent+Demographics • Cognitive Eval (MMSE) • Rate Pain (VAS & FACES) • Pain Medication Use Survey • EEG (4 min)
V1-5 Week 2	
 • Pre-session survey • Vitals • Rate Pain using VAS and FACES • Pre-EEG (2 min) • tDCS1 - .5mA to .75mA (5 min) → EEG (8 sec) • tDCS2 - .75mA to 1.0mA → EEG (8 sec) • tDCS3 - 1.0mA to 1.75mA (10 min) → EEG (8 sec) • Post-EEG (2 min) • Vitals • Rate Pain using VAS and FACES • Side-Effect Self-Report Survey 
*For the Sham group - the first 1 minute of every tDCS session they receive a negligible current titrated from 0mA up to and not to exceed .5mA to give the impression they are receiving the treatment. The remaining treatment times will be followed by no current.

V6 Final Day 11 Week 3	
 • MMSE • Rate Pain using FACES and VAS • Pain Medication Use Survey • EEG (4 min)

tDCS Application:

EEG: The tKIWI uses sensors placed on specific locations of the head for the EEG reading. The first time the headset is applied, our research staff will do some minor fitting. There are sensors that run along a strap front to back (base of skull to forehead) and another side to side (ear to ear). The device uses the standard 10-20 system for both location and names of the sensors. Flat sensors will be placed on the forehead. The headband should come down about a half inch above the eyebrows in front. Once all sensors are green, they are ready to record EEG data.

The hair and dry skin act as a resistor between the sensor and the skull. The more resistance the lower the amplitude of the measured signal. Normally this resistance which is also referred to as impedance in the literature is in the realm of 10-100K ohms. Ensuring a snug fit and moving the hair will decrease impedance and improve EEG readings.

IRB Protocol for Human Subjects Research

tDCS: The anode and cathode are two large 5 cm by 5 cm gel-based pads which are placed on the scalp. This reduces the risk of burn or irritation and increases conduction. The 2 electrodes are connected to the tKIWI device which delivers a low intensity electrical current ($\leq 2A$), thereby polarizing membrane potential of neurons in the stimulated area. Current that flows from the cathode to the anode has an inhibitory effect on the stimulated area, while current that flows from the anode to the cathode is typically excitatory. We will be initiating bilateral stimulation of the Dorsolateral pre-frontal cortex (DLPFC), which has been shown in the literature to elicit a significant decrease in ambiguous risk-taking behavior in healthy human subjects and a decrease in pain on a non-ambiguous risk task.

Both anodal and cathodal stimulation is used. Anodal is the negative or inhibiting electrode and cathode is the positive or oxidizing. tDCS is polarity-dependent.

In order to help minimize the stinging feel of the treatment, we have chosen to ramp up time and frequency. For visits 1-5 (tDCS treatment visits), we will start with .5mA ramping up to .75mA for 5 minutes. Followed by a brief (8 sec) EEG recording. Then, we will apply .75mA to 1mA for 5 minutes. This will also be followed by 8 second EEG recording. The final application of current will be 1mA to 1.75mA for 10 minutes followed again by 8 second EEG recording. The sham group will receive 1 minute from 0.0mA to no more than 0.5mA at the initiation of the treatment after which the current will be turned off. This is to maintain a blind trial. 0.5mA is negligible current, but mimics treatment with an initial small tingle. The current delivered by tDCS is not strong enough to trigger an action potential in a neuron; instead its “sub-threshold” changes the pattern of already active neurons. The device has built-in protections to prevent more than 2mA from being inadvertently administered at any time. The Clinical Trial Protocol table demonstrates the study procedures for each day.

Vitals (heart rate, pulse, blood pressure, temperature) will also be taken at the beginning and end of each treatment visit along with an open-ended verbal self-report of any side-effects, which the researcher will document in redcap.

- **Specify the total estimated time commitment for subject participation, and the estimated time commitment for each activity.**

The estimated time commitment for this study is 11 days and approximately 1.5 hours each day over 3 weeks.

- **If any biological specimens (blood, urine, tissue, etc.) are being collected for research, state the amount, method, frequency, and type of specimen to be collected and what the specimen will be used for.**

NA

If the study is a [clinical trial](https://clinicaltrials.gov/), confirm registration with <https://clinicaltrials.gov/> has been completed:

This study is not a clinical trial:

Registration complete:

Registration pending:

Responsible Physician Limited Role:

IRB Protocol for Human Subjects Research

[name] will be available via telephone during all treatment sessions. There is no medical or safety need for a physician to administer the tDCS treatment or be present during the tDCS treatments. The application of tDCS is relatively straight forward, using materials that require very minimal training, the treatment is known to be non-invasive and safe, and is widely available on the market for personal home-use. In the proposed study, we will monitor vitals that can be properly done by a lay person. Should any of the most commonly reported side-effects occur, literature indicates the side-effects would not require medical intervention (other than basic first aid) nor a physician to attend to the subject. [name] skills in family medicine and addiction will be instrumental in guiding this study from a medical lens. [name] skills in neuroscience and addiction will be instrumental in guiding this study from neuro-psychological and neuroscience lens. [name] skills in addiction and artificial intelligence will be instrumental in guiding from the technical and behavioral health lens. The tKIWI device has built in safety features to limit the current to +2 or -2 milliamp (mA). These values have been medically shown, over 50 years, to be well within the range that is safe for the treatment of the brain by modulating the neurons but not causing the direct firing of a neuron. A research assistant will be trained on the tKIWI and set up the device. Drs. [name] or [name] will be present during administration of tDCS. [name] is a practicing physician and will be responsible for monitoring any reported side-effects and interacting with subjects who have questions during the consenting process. Experience of prior studies indicate It is medically and academically unnecessary for her to be present during the treatment sessions, but she will be available telephonically during treatment sessions.

There is a breadth of literature that demonstrates the safety and efficacy of administering tDCS and tCES [8-10,12, 16-18, 32-33]. tDCS has been studied for decades as a promising adjunctive therapy for numerous degenerative brain diseases and disorders due to its ability to modulate neural activity in the human brain painlessly and non-invasively. The literature indicates side effects are minor and transient [18, 32-33]. In fact, only one major adverse event has been reported in the scientific literature related to employing tDCS treatment, which involved a pediatric patient with pre-existing epilepsy and cerebral palsy [34]. In a letter to the Editor, the author of that single case study states, "Unlike transcranial magnetic stimulation, tDCS does not induce neuronal firing by suprathreshold stimuli. Induction of seizure by tDCS has not been reported previously. On the contrary, cathodal stimulation was reported to be well tolerated in children with epilepsy, and is associated with a decrease in seizure frequency" [34]. The case study indicated this patient "remained seizure free with valproate and topiramate, but developed left dominant spastic paresis. He had his last seizure during a viral infection at 3 years of age. Interictal EEG showed absence of active epileptiform discharges. Dosage of valproate was adjusted to 30 mg/kg and topiramate was tapered. Two weeks after completion of topiramate tapering, anodal stimulation with 25-cm² electrodes was initiated to right motor cortex for 20 minutes at 1.2 mA." The patient had a seizure 4-hours after his third tDCS treatment and remained seizure free once treatment ceased. The single case study also indicates, "The possible etiologies of the induction of seizure after tDCS in this patient might be related to recent adjustment in antiepileptic treatment regimen, premedication with escitalopram, or anodal stimulation."

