Research will be conducted at the UArizona Comprehensive Pain and Addiction Center in [name] lab room 641 with the full support and funding of Family and Community medicine. The CPAC has all the resources required to fulfill this study. We will hire a research coordinator in addition to the PI and Co-I.

Timeline of Study:

Phase	Milestone	Start/Finish	Tasks Overview
Phase 1 Planning Months 1-6	Finalize Clinical Protocol	Month 1 - 2	
 Work with FDA consultants, [name], study coordinator and other personnel to finalize protocol
	Regulatory Approval	Month 1-2	
 Submit UArizona IRB Submit UAHS Contracts Submit IDE application to the FDA Submit to DOD Human Research Protection Office [HRPO]
	Recruitment strategies meetings	Month 1-3	
 Establish access to patient populations Work with clinical network, local enterprises, and providers Develop marketing material, informed consent etc.
	Finalize tKIWI units and software for clinical trial	Month 3-6	
 Adapt tKIWI software for double blind clinical trial, prepare for data anonymization, HIPAA etc. Manufacture 4+ tKIWI systems in different sizes Prepare for data collection and storage
	Training	Month 6	
 Train Clinical Research Coordinator, Study Coordinator, Research Assistants on administering tKIWI blinded, monitoring vitals, administering questionnaires etc.
Phase 2 Clinical Trial Month 7-20	Recruit Patients	Month 7+	
 Recruit 40 chronic pain patients Informed consent Medical questionnaires/surveys etc.
	Baseline Session and Preparation for data collection	Month 10+	
 Collect baseline EEG readings Create patient profiles, anonymize personal information Randomize treatment assignment Preliminary EEG biomarker analysis

IRB Protocol for Human Subjects Research

	Clinical trial (2 weeks)	Month 11-12	
 Each patient has one daily treatment session (blinded treatment or sham)
	Follow up	Month 12-13	
 Follow up with each patient one week and two weeks after clinical trial
	Statistical analysis	Month 14	
 Statistical analysis of data collected including questionnaires, vital monitoring, EEG etc. Publish findings in an academic journal Transition plan for next phase of clinical trial

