	Publish	Month 16	
 Publish findings in an academic journal Present findings internally and at conference Plan for next phase of clinical trial Publish biomarkers data in academic journal
	Transition	Month 17+	
 Prepare and submit R01

6.0 Study Population:

- Select all the categories of participants included in the research:

 Healthy adults	 Non-English-speaking subjects
 Non-healthy adults	 UA staff/faculty
 Children (under 18 years old) *	 UA students
 Pregnant women, neonates, and/or fetuses*	 Banner employees
 Prisoners*	 Refugees
 Native Americans, Alaskan Native, and Indigenous Populations*	 Other – please explain: Adults ages 18-79 with a self-reported history or diagnosis of chronic pain (>3mo)
 Adults unable to consent (i.e., cognitively impaired adults) *	

- For each of the above selected categories, describe the inclusion and exclusion criteria. Indicate age range, gender, and ethnicity.

Inclusion Criteria:

Age: 18-79 years old

Gender: Any

Ethnicity: Any

Chronic pain (\geq 3-months); No current use of nonprescription opioids (\leq 1 month); Able and willing to comply with scheduled visits and other study-related procedures to complete the study; Willing and able to give informed consent.

Exclusion Criteria:

- Diagnosis (as defined by DSM-IV) of: any psychotic disorder (lifetime); eating disorder (current or within the past year); obsessive compulsive disorder (lifetime); mental retardation.

IRB Protocol for Human Subjects Research

- History of drug or alcohol abuse or dependence (as per DSM-IV criteria) within the last 3 months (except nicotine and caffeine).
- Subject is on regular benzodiazepine medication which it is not clinically appropriate to discontinue.
- Subject requires a rapid clinical response due to inanition, psychosis or high suicide risk.
- Neurological disorder or insult, e.g., recent stroke (CVA), which places subject at risk of seizure or neuronal damage with tDCS.
- Subject has metal in the cranium, skull defects, or skin lesions on scalp (cuts, abrasions, rash) at proposed electrode sites.
- Female subject who is pregnant.

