Recruitment Location(s): We plan to recruit participants from clinical settings in Tucson, Arizona, such as the Veterans Affairs Hospital and private clinics and hospitals, private enterprises, such as gyms and health-related facilities (chiropractic offices, yoga/pilates studios). We also plan to recruit participants via local Facebook/Instagram and Twitter.

Recruitment Method(s): Recruitment flyers will be distributed to several health clinics and settings. Additionally, ads will be placed on Facebook and Twitter. At this time, we do not plan to conduct in-person recruitment. The flyers will include a link and QR code to a simple Qualtrics form where the interested person will be able to include their name and contact information. Potential participants will then be contacted to schedule an initial visit.

Site authorizations will be sought for each place we put flyers.

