Discuss the amount of compensation (monetary and/or non-monetary) subjects may receive. Describe if compensation will be prorated.

Patients will receive \$175 in compensation for their time. We will prorate payments based on duration of participation in the research so that participants are able to receive compensation even if they do not complete the entire study. In doing so, each participant will receive \$25 cash at the initial visit (V0), \$50 in cash after their 4th (V3) visit, and \$100 after their final visit (V6).

12.0 Privacy of Subjects and Confidentiality of Data:

- **Describe steps, if any, to protect the privacy of the subjects throughout their participation (e.g., during the recruitment process, consent process, and/or research procedures).**

The raw identifiers will be de-identified by the research coordinator. Each subject will receive a number and the only connection between the identifiers (name, DOB, contact information) and the number assigned each subject will be safe-guarded in a unique UA Box Health. The microdata that will be collected using the tKIWI will all be housed within the device and is deidentified data. The risk is minimal to connect the EEG readout and self-report surveys, data related to vital monitoring, consents, and any other data collected, as the only data held within the tKIWI is the EEG date and study ID. The raw data will be stored in a unique UA Box Health folder. All data will be uploaded and stored in a secure and unique folder hosted on UA Box Health. tKIWI device data will be uploaded to a Google Workspace that is HIPAA compliant.

Describe if data or specimens will be kept for future research, including unspecified future research and genetics. If data or specimens will be stored in a repository, indicate who holds the repository and what information will be sent to the repository. Ensure this information is reflected in the subject's informed consent form.

The deidentified raw data will be stored for future research. The results will be published and shared with industry partner, ni20, inc., as per our data sharing agreement.

- **Discuss how study results will be shared with subjects, families, and/or the institution, both immediately and long-term.**

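### Does the plan need to name who draws the allocation lottery and how the result is kept from enrolling staff?

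*Combined protocol and SAP*

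**What the plan says.** The randomization procedure is in section 10.0, under the description of research procedures. Allocation is 1:1, and the text says that "each participant will be assigned to a condition independently of the other participants. The sample is small (20 each group"). Every participant gets a unique number. "Then, we will use a lottery method to randomly assign each number to the control or experimental group." The only actor is the study team as a whole.

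Other sections bear on the draw without describing it:

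- **Timeline of Study (5.0).** Randomization appears among the baseline-session tasks, below the baseline EEG, with no role attached. The planning phase includes adapting the device software for a double-blind trial and the task "Train Clinical Research Coordinator, Study Coordinator, Research Assistants on administering tKIWI blinded".
- **Risks to Subjects (after 11.0).** Research staff give each person a study number on enrolment.
- **Privacy (12.0).** "The raw identifiers will be de-identified by the research coordinator. Each subject will receive a number".
- **Screening and visits (10.0).** Screening takes place in REDCap, where "the potential participant will respond to inclusion and exclusion criteria". Participants also answer a short survey at the start of each visit, "to ensure no changes to eligibility have occurred between visits".
- **Recruitment (7.0).** "Potential participants will then be contacted to schedule an initial visit".
- **Exclusion criteria (6.0).** Some need judgement, for example "Subject is on regular benzodiazepine medication which it is not clinically appropriate to discontinue".

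**The concern.** Concealment differs from blinding. Blinding protects delivery and assessment after allocation; concealment protects entry before it. The plan describes the first (sham current, adapted software, trained staff) and says nothing explicit about the second. Redaction does not explain the silence, because the lottery sentence is complete and contains no removed name.

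The team is small: one hired coordinator with the principal investigator and co-investigator, plus research assistants named in the training task. The same people could therefore schedule, enrol, code and recheck participants. If any of them could see the draw, knowledge of the arm might affect who enters or who starts treatment. The two-sample tests in the Data Analysis text could neither detect nor correct that.

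There is also a loose end in the wording. Independent assignment does not guarantee 20 per group, so it is unclear whether the split is a target or is fixed.

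**Working it through.** The documents give no figure on concealment, so there is nothing of the plan's own to reproduce. The check has two parts: the order of events, then the possible size.

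**1. Order of events**

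| Step | Section | Could staff know the arm? |
|---|---|---|
| Contact and scheduling | 7.0 | No number exists yet, so none has been drawn |
| Screening, self-answered in REDCap | 10.0 | As above |
| Enrolment; number issued | Risks to Subjects | The number exists; the lottery acts on it afterwards |
| Baseline EEG, then randomization | 5.0 | The arm is first fixed here |
| Visits 1–5; participant answers the eligibility survey | 10.0 | Treating staff are to be blinded |

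On this reading the judged exclusion criteria and the scheduling calls come before the draw. Two assumptions carry it: that the number drawn in the lottery is the study number issued at enrolment, and that the timeline's task order is the working order.

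**2. Size if the draw were visible (assumptions, not document figures)**

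Suppose a share *s* of each arm is steered between people whose expected pain change differs by 0.5 SD: +0.25 SD in the active arm and −0.25 SD in the sham arm. The arms then differ by 0.5 × *s* with no treatment effect. For a two-sided 5% t-test with 20 per arm, the noncentrality is difference × √(20 × 20 / 40) = difference × 3.162.

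| *s* | Difference (SD) | Noncentrality | Rejection rate |
|---|---|---|---|
| 10% | 0.05 | 0.158 | 5.3% |
| 20% | 0.10 | 0.316 | 6.1% |
| 40% | 0.20 | 0.632 | 9.5% |

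**3. Would a fixed 20/20 list be better?**

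- *Balance.* Under independent assignment, P(exactly 20/20) = C(40,20)/2^40 = 0.125. A split more uneven than 16/24 has probability 0.154.
- *Power.* Take an assumed effect of 0.909 SD, which gives 80% power at 20/20. At 16/24 the noncentrality factor falls from 3.162 to √(16 × 24 / 40) = 3.098, and power is 78.4%.
- *Predictability when past allocations are known.* Independent assignment gives 20 correct guesses of 40. One 20/20 list gives n/2 + 2^(n−1)/C(n, n/2) − 1/2, which at n = 40 is 20 + 3.99 − 0.5 = 23.5. Four blocks of 4 and four of 6 give 4 × 2.833 + 4 × 4.1 = 27.7.

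The list therefore buys about 1.6 percentage points of power against a 16/24 split, at the price of more predictability. It also puts assignments in existence before anyone enters.

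**The case for a change.** The strongest case for a change is that the order of events is inferred. The timeline is a task list, not a stated sequence. If the lottery is a 20/20 draw made one person at a time with earlier results known, guesses are right 23.5 times in 40 and the last assignment is certain. Even with a single draw over an assembled sample, somebody must hold the result while eligibility is rechecked at each visit. Anyone holding both the number link and the lottery result would know every arm, and the researcher also records the open-ended side-effect reports used for Aim 3. Concealment cannot be restored afterwards, and one sentence would cost little.

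Part of this stands: the custodian is unnamed, and the order is not stated outright. But the rechecks are participant-answered surveys that open the same visits at which staff are meant to be blinded. A team that keeps its declared double-blind design must already hold the allocation away from those staff. The predictability worry requires a one-at-a-time draw without replacement, whereas the text calls assignments independent; on that wording past results say nothing about the next.

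**Conclusion.** The omission is real, but it is missing operational detail and not a flaw in the design. Read together, sections 5.0, 10.0 and Risks to Subjects put the draw after enrolment and baseline, so the gap concerns custody of the result after the draw, not who enters the trial. A team running a double-blind study would settle custody in its working procedures.

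The possible harm ranges from negligible to modest: 5.3% to 9.5% false positives against 5%. The upper end needs 40% of both arms steered, which is hard to square with self-answered screening and a draw after enrolment. Both the steering share and the 0.5 SD gap are assumptions.

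Whether 20 per group is a target or a fixed split is a point of wording. Unequal arms would not bias the comparison and would cost little power (78.4% against 80% at 16/24). Replacing the lottery with a prepared 20/20 list is a defensible preference, but it removes no demonstrated bias. The conclusion rests on the lottery number being the enrolment study number and on the planned staff blinding being kept.
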